## CHAPTER I

### INTRODUCTION

Epidemiological data shows that 46 % of adults suffer from various foot conditions that result in abnormal mechanics of standing and walking. Chronic heel pain might impair walking and cause spinal pain. Plantar heel pain is one of the most common musculoskeletal disorders of the lower extremity that affects about 10% of the general population, associated with limitation on activity, depression, and reduced health related quality of life (**Krukowska et al., 2016**)(**Cotchett et al., 2016**).

A calcaneal spur is an abnormal undesired calcium deposits on the heel bone, this process usually chronic process that continues for many months. The treatment of calcaneal spur is primarily conservative. However, Surgery and corticosteroid therapy is a line of treatment in severe cases. (**Lizis et al., 2017**).

Conservative treatment includes non-steroidal anti-inflammatory drugs (NSAIDs), physiotherapy modalities such as electrotherapy (microwaves, extracorporeal Shockwave (ESWT), Ultrasounds, Transcutaneous electrical nerve stimulation (TENS), short waves, Iontophoresis, phonophoresis, interferential and pulsed electromagnetic therapy) (**Cuadros, 2016**).

Extracorporeal shockwave therapy (ESWT) is now extensively used in the treatment of musculoskeletal disorders, For example, chronic diabetic and non-diabetic ulcers ,calcifying tendinitis of shoulder, planter fasciitis and lateral epicondylitis, from approximately 20 years with

successful rate ranged from 65% to 91% (**Frairia & Berta, 2011**) (**Wang, 2012**).

Many researchers investigated the effect of shockwave therapy in the management of proximal plantar fasciitis and conveyed a success rate ranging from 34% to 88%. (**Wang, 2012**).

The interaction of shockwave with biological cells is a new area of research. For example, water purification, desalination, and bacterial decontamination. Shockwave also have great potential for biomedical use, since they can also permeabilize cell membranes thereby allowing for the transport of various macromolecules, drugs and genetic material into cells. in addition to that extracorporeal Shockwave lithotripsy (ESWL) used to treat kidney stones below 20 mm in size, or destruction of cancer cells (**Hu et al., 2019**).

Marcos et al., conducted a research about the effect of 5% Acetic Acid Iontophoresis and Ultrasound over calcified Achilles Tendon. The result showed that Iontophoresis with 5% Acetic Acid and Ultrasound is a safe, simple and inexpensive modality able to reduce significantly pain and size of calcification on the ankle (**Marcos et al., 2019**).

Acetic acid is one of the most important substance used in physical therapy to treat abnormal calcification via introducing it by phonophoresis or iontophoresis because it promotes a chemical reaction capable of forming a compound more soluble, which facilitates the calcium absorption. Pamplona E et al., report a case study in which he apply (5% acetic acid) phonophoresis for calcified shoulder joint was effective in the treatment of

calcific tendinitis of supraspinatus muscles , improving the ROM, muscle strength and functional capacity, in addition to eliminating the pain of the affected shoulder (**Pamplona et al., 2017**).

### ➤ **Statement of the Problems:**

There is a gap in literature on the effect of Shockwave in combination with substance like acetic acid gel on treatment of calcaneal spur patients. So, this study conducted to answer the following question:

- Dose the extracorporeal acetic acid shockwave phonophoresis has any effect on length of calcaneal spur, pain pressure threshold, pain level and physical function in patients with calcaneal spur?
- Dose the extracorporeal shockwave has any effect on length of calcaneal spur, pain pressure threshold, pain level and physical function in patients with calcaneal spur?
- Is there a statically significant difference between extracorporeal shockwave and extracorporeal acetic acid shockwave phonophoresis on length of calcaneal spur, pain pressure threshold, pain level and physical function in patients with calcaneal spur?

### ➤ **Purposes of study:**

The aims of this study is:

- To investigate the effect of extracorporeal acetic acid shockwave phonophoresis on length of calcaneal spur, pain pressure threshold, pain level and physical function in patients with calcaneal spur.

- To investigate the effect of extracorporeal shockwave on length of calcaneal spur, pain pressure threshold, pain level and physical function in patients with calcaneal spur.
- To investigate and compare the efficacy of extracorporeal shockwave versus extracorporeal shockwave acetic acid phonophoresis in patients with calcaneal spur.

➤ **Significance of the study:**

The painful heel is a common musculoskeletal problem that affects the general population in their lifetime especially runners (**Perez et al., 2003**). Local application of the drug is faster, increased comfort of the patient, improve the effectiveness of the treatment, and decreases the hazards of systematic side effect of the Like gastrointestinal tract problems and decrease the efficacy of the treatment.

Iontophoresis with 5%Acetic Acid and Ultrasound is a safe, simple and inexpensive technique and effective treatment capable to reduce pain and calcification on the shoulder, elbow, wrist, hip, knee and ankle (**Cuadros, 2016**).

The biochemical theory of the process has been described in detail where the use of acetic acid iontophoresis converts insoluble calcium carbonate in chronically inflamed tissue to calcium acetate, which is soluble in blood. Pulsed ultrasound was used to reduce inflammation, improve local blood flow that facilitate the removal of the newly formed calcium acetate into the blood, and thereby remove it from the localized area of heel pain (**Costa & Dyson, 2007**).

The effect of shockwave and the ultrasound has been compared on feet pain and quality of life in the patients with calcaneal spur. There was a significant improvement in the feet pain and quality of life. However, the patients treated with shockwave had significantly greater pain decrease and life quality improvement, and those benefits were still present three months after the treatment (**Lizis & Hudáková, 2016**).

Shockwave could be used as a pretreatment of cell membranes for electroporation. The Shockwave possible role of multiple Nano bubbles was examined. It has also been shown that not only would the multiple Nano bubbles make it possible to create larger pores, but also increase the pore density on the surface. The multi-pore scenario would be useful practically in enhancing material throughout into cells. (**Hu et al., 2019**).

Direct and indirect Shockwave effects described concerning stone disintegration could also contribute to transient increase membrane permeability on application of low energy shockwave to eukaryotic cell membranes. Low energy shockwave can deliver macromolecules of up to 2,000,000 molecular weight into the cytoplasm of cells. (**Tyagi & Chuang, 2018**).

Low energy shockwave has a significant effect on the permeability of tissue. Consequently, it might be used to deliver substance such as Acetic acid. Accordingly, Shockwave might help to improve the outcomes with calcaneal spur patients. Therefore, the present study might help in treatment of calcaneal spur patient and might improve the quality of life in fast and efficient way.

➤ **Delimitations:**

This study will be delimited to calcaneal spur patients, selected from outpatient clinics at faculty of physical therapy on Beni-Suef University on the following criteria:

1. The patient's age ranged from 30 to 65 years
2. Patients with calcaneal spur.
3. Patients with intact sensory perception.
4. At least 6 weeks from last corticosteroid injection; 4 weeks from the last local anesthetic injection, iontophoresis, ultrasound, and electrotherapy (**Gerdesmeyer et al., 2008**)
5. X-Ray will be used to measure the length of calcaneal spur.
6. Algometry will be used to measure Pain pressure threshold.
7. Visual Analogue scale will be used to measure Pain intensity level.
8. Foot and Ankle Ability Measure (FAAM) questionnaire will be used to measure physical function.

➤ **Basic Assumptions:**

The following assumptions are necessarily for the development of the study:

- The instructions that will give to all patients for assessment should be accurately, clearly, and faithfully followed.
- All patients will be cooperative during the assessment and treatment procedures.

➤ **Hypothesis:**

The null hypotheses of this study stated as the following:

- $H_0$  : there is no statistical significant effect of the use of extracorporeal acetic acid shockwave phonophoresis on length of calcaneal spur, pain pressure threshold, pain intensity level and physical function in patients with calcaneal spur.
- $H_0$ : there is no statistically significant effect of the use of extracorporeal Shockwave on length of calcaneal spur, pain pressure threshold, pain intensity level and physical function in patients with calcaneal spur.
- $H_0$ : there is no statistically significant difference between extracorporeal shockwave versus acetic acid shockwave phonophoresis on length of calcaneal spur, pain pressure threshold, pain intensity level and physical function in patients with calcaneal spur.

➤ **Definition of terms:**

The following terms defined for clear understanding of the terminology used in the presented study:

**Calcaneal spur:** is an osteophyte outgrowth just medial process of calcaneal tuberosity.

**Shockwave:** is an acoustic wave characterized by high positive pressures of more than 1000 bar (100 MPa), which can be developed within an extremely short rise time ( $10^{-9}$  seconds) and followed by a low-pressure phase of tensile stress equivalent to 100 bar (10 MPa).

**Energy flux density:** is a term used to reflect the amount of energy delivered to a specific area of tissue. measured in (Mj/mm^2) (**Speed C , 2014**)

**Enthesis** is the site of attachment of tendon, ligament, fascia, or capsule to bone.

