#### **1. Design of the study:**

Double-blinded pretest posttest randomized control design will used.

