#### **2. Subjects:**

The age of participant will range from 30 to 65 years. These patients will be allocated from the outpatient clinic in faculty of physical therapy at Beni-Suef University. The purpose, nature and potential risk of the study will be explained to all participant and they will sign a written informed consent prior to participation (**Appendix I**). Forty patients from both gender will be involved in this study and will randomly subdivided into two equal groups in number:

**Group (A):** (experimental group 1) this group composed of 20 subjects represented the experimental group 1. They will receive 6 sessions acetic acid shockwaves phonophoresis with Time between sessions 5-7 days plus exercise and dietary advice.

**Group (B):** (experimental group 2) this group composed of 20 subjects and represented the experimental group 2 who will receive 6 sessions of Shockwave plus exercise and dietary advice.

**Group (C): (Control Group):** This group composed of 20 subjects they will take conventional physical therapy program (Exercise)

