**b. Therapeutic Equipment:**

1. Shockwave apparatus: Gymna Shockmaster 500 device will be used in this study. This device is a radial shockwave device, pneumatically generated and composed from (**Fig12**): Device Shockmaster 500, Communicating Wire between applicator and device, Hand piece applicators that is light ergonomically well design hand piece applicator, D-Actor 20 mm applicator and Trolley Shockmaster 500. The device allow variability in the setting with Frequency range 0,5 - 21 Hz and Pressure range 0,3 - 5 bar.
2. Acetic acid gel: 5% concentration acetic acid gel form will be applied to the foot as a coupling media instead of ultrasound gel between the applicator and the body surface (**Pamplona et al., 2017**).
3. Exercise program: designed to adjust foot mechanics by stretch tight structure and strength the weak muscles.
4. Advices: Dietary advices and advices to alter calcaneal spur pain.

**Figure 12:** shockwave apparatus adapted from <https://gymna.com/en/products/shockwave-therapy/gymna-shockmaster-500>

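### As written, Group C lacks the dietary advice given to Groups A and B, so the two control contrasts that could answer the first two hypotheses mix shockwave with advice; those hypotheses also name no comparator.

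*Combined protocol and SAP*

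**What the plan says.** **Hypotheses.** Chapter I, Hypothesis, states first that "there is no statistical significant effect of the use of extracorporeal acetic acid shockwave phonophoresis on length of calcaneal spur" (and on the other three outcomes), then the same for shockwave alone. The third hypothesis compares the two shockwave regimens with each other. The research questions and aims follow this pattern, for example "Dose the extracorporeal shockwave has any effect on length of calcaneal spur" and "To investigate the effect of extracorporeal shockwave on length of calcaneal spur". None of them mentions Group C.

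**Design and arms.** Chapter III states "Double-blinded pretest posttest randomized control design will used". The Subjects section says "Forty patients from both gender will be involved in this study and will randomly subdivided into two equal groups in number", then defines three groups of 20 and labels C the control group. Group A receives acetic acid shockwave with exercise and dietary advice. Group B is the group "who will receive 6 sessions of Shockwave plus exercise and dietary advice". For Group C, "they will take conventional physical therapy program (Exercise"). The list under Therapeutic methods, Shockwave therapy, again gives C exercise only.

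**Advice.** Therapeutic Equipment lists "Advices: Dietary advices and advices to alter calcaneal spur pain" without naming arms. The later Advices section describes pain advice (rest, shoes, activity, ice) and dietary advice (gout, body weight), again without naming arms. The stretching section places an ice-bottle home measure inside the exercise program.

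**Analysis.** Statistical Analysis plans a two-way mixed MANOVA for normally distributed data, Kruskal-Wallis and Mann-Whitney tests otherwise, and Bonferroni pairwise comparisons. No contrast is linked to a hypothesis. Measurements are planned before treatment, after treatment and at one month.

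**The concern.** The first two hypotheses ask whether shockwave works, with and without acetic acid. Only a comparison with a randomised group that differs in shockwave alone can answer that. As the arms are described, C differs from A and B in dietary advice too, so a difference from C could not be credited to shockwave alone.

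Because the hypotheses name no comparator, a second route to an answer stays open. On the mixed-MANOVA branch, the change over time within an arm could be reported as the effect of shockwave. That change also contains exercise, advice and natural course.

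Finally, if the data go down the non-normal branch, the group comparison as described makes no use of the baseline values, which gives up precision in a small trial.

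**Working it through.** **Step 1: break the arms into components, as written.**

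| Arm | Shockwave | Gel | Exercise | Dietary advice |
|---|---|---|---|---|
| A | yes | 5% acetic acid | yes | yes |
| B | yes | ultrasound gel | yes | yes |
| C | no | none | yes | not listed |

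Write s for the shockwave effect, g for the added effect of acetic acid gel and d for the effect of dietary advice, and assume they add. Then:

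- A minus C = s + g + d
- B minus C = s + d
- A minus B = g

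Advice cancels only in A minus B. Each control contrast is off by the whole of d.

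**Step 2: what d could do.** The documents give no value for d. Purely as an assumption, take d = 0.1, 0.2 or 0.3 SD with no shockwave or gel effect. A baseline-adjusted A-C test at 0.0167 then rejects in 2.4%, 4.6% or 9.0% of trials at a pre-post correlation r of 0.5, instead of 1.7%. For r from 0.3 to 0.7 the ranges are 2.2-2.7%, 4.1-6.2% and 7.6-13.2%. If d is zero, nothing is lost.

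**Step 3: which planned analysis answers the first two hypotheses.** With three arms there are three pairs: A-C, B-C and A-B. The planned pairwise comparisons can produce all of them, but none is assigned to a hypothesis. The plan names no within-arm test, and the Kruskal-Wallis/Mann-Whitney branch contains none. The mixed MANOVA has a time factor, so a within-arm time effect is available there.

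**Step 4: what use of baseline is worth.** The plan has no sample-size calculation to reproduce. Inputs: 20 per arm (Subjects); two-sided 0.05 (Statistical Analysis) divided by three pairs, 0.05/3 = 0.0167; outcome SD = 1; r assumed at 0.3, 0.5 and 0.7. Power is from the noncentral t distribution.

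- Baseline-adjusted post value: SE = sqrt((2/20)(1 - r²)), df 37. At r = 0.5, SE = sqrt(0.1 × 0.75) = 0.274.
- Group-by-time change: SE = sqrt((2/20) × 2(1 - r)), df 38. At r = 0.5, SE = sqrt(0.1 × 1) = 0.316.
- Post value alone: SE = sqrt(2/20) = 0.316 at any r, df 38. For Mann-Whitney, divide the detectable difference by sqrt(0.955), its relative efficiency for normal data.

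Difference detectable with 80% power, in SD:

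| r | Adjusted | Change | Post only, t test | Post only, Mann-Whitney |
|---|---|---|---|---|
| 0.3 | 1.02 | 1.26 | 1.06 | 1.09 |
| 0.5 | 0.92 | 1.06 | 1.06 | 1.09 |
| 0.7 | 0.76 | 0.82 | 1.06 | 1.09 |

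Adjustment is the most precise option at every r tried. The group-by-time contrast only equals the post-value t test at r = 0.5 and is worse at r = 0.3.

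**The case against.** **The comparator can be inferred.** The design is described as randomised and controlled, C is labelled the control group, and pairwise comparisons among three arms give exactly A-C, B-C and A-B, one for each hypothesis. This largely stands: what is missing is a linking sentence. A reader might infer that the plan intends to judge shockwave by before-after change within each arm, or that the first two hypotheses cannot be tested at all. The documents support neither on the three-arm reading, since no within-arm test is named as deciding them and the control contrasts can be produced.

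**The advice may have been meant for everyone.** The materials and Advices sections restrict advice to no arm, and a conventional program could include it. This stands as a possibility, so a reader should not conclude that C will certainly receive no advice. But both descriptions of C list exercise only, while A and B have advice added by name.

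**The difference is narrow.** The Subjects section adds only dietary advice, in patients whose body mass index must be below 30. Rest, shoes, activity and ice are assigned to no arm. This stands, and it is why no claim is made that the bias is large.

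**Equal advice would not make the control contrasts clean.** C has no sham, so A-C and B-C would still include treatment contact and expectation, which matter for pain, function and algometry. This stands as a limit on the fix.

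**The new question is untouched.** The gap the protocol names is shockwave combined with acetic acid, which A minus B addresses. This is correct.

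**Conclusion.** The point holds in a limited form and should be fixed. On the three-arm reading, following the arm definitions as written makes A-C and B-C contrasts of shockwave plus dietary advice. The resulting bias equals the advice effect, whose size is undocumented and may be near zero. The third hypothesis is unaffected.

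The missing comparator is mainly a gap in wording: the rest of the plan points to A-C and B-C, but a within-arm time effect is not ruled out as the answer.

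The gain from baseline adjustment is a detectable difference of 0.92 SD against about 1.06-1.09 SD for post values alone. It rests on an assumed r of 0.5, normal data, 20 complete patients per arm and three pairwise tests.

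All of this depends on there being three arms. The wording about forty patients in two groups conflicts with that. If the trial has only Groups A and B, there is no control arm and the first two hypotheses have no randomised comparator.

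**What to change.** 1. Confirm three arms of 20.
2. Give all three arms the same exercise and the same advice, and say so in Subjects, Therapeutic methods and Advices. The sponsor chooses the common package.
3. Define the first hypothesis as A minus C, the second as B minus C and the third as A minus B.
4. Decide each by a between-arm contrast that accounts for baseline, at 0.05/3 per outcome and time point. Use ANCOVA on the post value (preferred for precision) or the group-by-time contrast of the planned mixed model. On the non-normal branch, use rank ANCOVA.
5. Report within-arm p-values as descriptive only.
6. State as a limitation that C has no sham, so A-C and B-C include contact and expectation.

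If the trial proves to be two-arm, remove the first two hypotheses or relabel them as descriptive within-arm change.

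**Cost.** Rewording, a little staff time to advise Group C, and, for ANCOVA, one extra model per outcome and time point. There are no extra patients, visits or X-rays. Even with adjustment, 20 per arm needs a large effect (0.76 to 1.02 SD for r from 0.7 to 0.3), so the first two hypotheses may not be rejected.

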## **CHAPTER II**

### **REVIEW OF LITERATURE**

This study conducted to investigate the efficacy of Shockwave phonophoresis on calcaneal spur patients.

In this part of the current study, the review of the related researches and studies of the main concepts presented under the following headings:

- Foot anatomy and calcaneal spur.
- Shockwave.
- Acetic acid and abnormal calcifications.

#### **1. Foot anatomy and calcaneal spur:**

##### **a. Foot anatomy:**

The foot consists of 26 bones, more than 30 articulations, more than 100 ligaments and 30 muscles act in foot segment. All of these joints must interact harmoniously and in combination to achieve a smooth motion. The foot moves in three planes, with most of the motion occurring in the rear foot; this will enabling three fundamental functions: supporting, shock absorbing, and weight bearing (**Woźniacka et al., 2013**)

The foot divided into three regions:

- The rear foot: consisting of the talus and the calcaneus.
- The mid foot: including the navicular, cuneiforms, and the cuboid.
- The forefoot : containing the metatarsals and the phalanges (**Standring, 2016**)

The tarsal bones arranged in a proximal and distal row, similar to the carpal bones in the wrist. The talus and calcaneus make up the proximal row in the foot, while the medial, intermediate, and lateral cuneiforms and the cuboid comprise the distal row. The navicular bone is interspersed between the talus and the cuneiform. The bones of the toes are very similar to the hand with the second through fifth toes consisting of metatarsal, proximal, middle, and distal phalanges. The first toe – similar to the thumb – does not contain a middle phalanx.

[figure not shown]
**b. Foot musculature:**

The foot and ankle are worked by both extrinsic and intrinsic musculature. The extrinsic muscles all originate from proximal to the foot. The intrinsic muscles of the foot originate and insert within the foot and act primarily on the toes. Their secondary function is to maintain postural balance through stabilization of the osteocartilaginous architecture of the foot.

The plantar muscles of the foot can be thought of as organized by layers from sole of the foot progressing deep to the bony structures. The first layer consists of muscles found just beneath the plantar aponeurosis – the flexor digitorum brevis, the abductor hallucis, and the abductor digiti minimi. These muscles extend from calcaneus to toes and create a functional group that assists in maintaining foot concavity. All three have been described as local pedicles muscle flaps, and all have type I vascular supply. The flexor digitorum brevis is supplied by branches of the posterior tibial artery via the medial and lateral plantar arteries on its proximal deep surface. The abductor hallucis is supplied by a dominant pedicle on its deep surface and by a branch of the medial plantar artery in the proximal foot. The abductor digiti

minimi muscle receives its dominant pedicle from a lateral branch of the proximal lateral plantar artery.

[figure not shown]
The first layer for the plantar foot is separated from the second layer by the tendons of the extrinsic muscles of the flexor digitorum longus and the flexor hallucis longus. Also, the medial and lateral plantar artery and nerve course in this intermediary plane (see Fig 1). (Paulsen, 2019)

**Figure 1:** the first layer of foot muscles (the outer layer) adapted from (Paulsen, 2019)

[figure not shown]
The second layer consists of the quadratus plantae muscle and the lumbricals muscles of the foot. The quadratus plantae is one of the few

muscles of the foot that does not have an similar structure in the hand. It has two heads extending from the medial and lateral border of the calcaneus, inserts into the tendon of the flexor digitorum longus, and aids in plantarflexion of the second to fifth toes. The lumbricals of the foot mirror those of the hand in their unique attribute of both originating and inserting on tendons. These four muscles arise from the medial side of the flexor digitorum longus and insert on the extensor system of the second through fifth phalanges .The foot lumbricals follow the same course as those of the hand and flex the metatarsophalangeal joints and extend the interphalangeal joints (see **Fig 2**).

**Figure 2:** the second layer of foot muscles (the middle layer) adapted from(Paulsen, 2019)

The third layer consists of the flexor hallucis brevis, the adductor hallucis, and flexor digiti minimi brevis. These form a small, deep intrinsic musculature that contributes in the maintenance of the longitudinal plantar arch and participates in the stabilization of intrinsic foot osteoligamentous intercalation and balance (see **Fig 3**).

**Figure 3:** the third layer of foot muscles adapted from(Paulsen, 2019)

The fourth layer is the interosseous compartment that contains both the plantar and the dorsal interossei. The three plantar interosseous muscles adduct the toes. The four dorsal interosseous muscles abduct the toes. The adduction–abduction activity of the interossei is based through the axis of the second toe, making this toe the least mobile at the metatarsophalangeal

joints. Tendons of the tibialis posterior and the peroneus longus are considered part of the fourth layer (see **Fig 4**).

**Figure 4:** the fourth layer of foot muscles adapted from(Paulsen, 2019)

The dorsum of the foot contains two muscles – the extensor digitorum brevis and extensor hallucis brevis. These muscles perform accessory toe extension function to the extrinsic toe extensors. The loss of these muscles does not significantly affect toe extension or impede ambulation. The extensor digitorum brevis extends the second through fifth toes while the extensor hallucis brevis extends the great toe. The extensor digitorum brevis receives its blood supply from the lateral tarsal artery, a branch off the dorsalis pedis. The extensor digitorum brevis is a useful muscle flap for small skin defects of the proximal foot and ankle. It can also be used as joint interposition to prevent fusion in nearby tarsal joints (e.g., calcaneonavicular bar)(Kleiber, 2018)

